#### 9.6.1 Adverse Events

The Medical Dictionary for Regulatory Activities (MedDRA) version 22.0 or later will be used to code all events categorized as adverse events, to a system organ class and a preferred term.

The subject incidence of adverse events will be summarized for all treatment-emergent adverse events, serious adverse events, adverse events leading to withdrawal of investigational product and fatal adverse events.

Subject incidence of all treatment-emergent adverse events, **serious adverse events**, adverse events leading to withdrawal of investigational product, and fatal adverse events will be tabulated by system organ class and preferred term **in descending order of frequency based on total summary. Adverse events and disease related events will be summarized together** as defined in [Section 5.1](#).

Summary of treatment-emergent **adverse events will be tabulated by system organ class, preferred term, grade, relatedness and seriousness.**

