9.2.3.1.1 Time Period and Frequency for Collecting and Reporting Safety Event Information

9.2.3.1.1.1 Disease-related Events

Disease-related events are defined in [Appendix 4](#).

The investigator is responsible for ensuring that all disease-related events observed by the investigator or reported by the subject that occur after the first dose of investigational product(s)/study treatment/protocol-required therapies through the end of study are recorded using the Event CRF.

All serious disease-related events will be recorded and reported to the sponsor or designee within 24 hours. The investigator will submit any updated serious disease-related event data to the sponsor within 24 hours of it being available.

Disease-related events assessed by the investigator to be more severe than expected and/or related to the investigational product(s)/study treatment/protocol-required therapies, and determined to be serious, must be reported on the Event CRF as serious adverse events and recorded and reported per [Appendix 4](#) and [Section 9.2.3.1.1.3](#).

Disease-related events pre-defined for this study include AD.

9.2.3.1.1.2 Adverse Events

The adverse event grading scale to be used for this study will be the Common Terminology Criteria for Adverse Events (CTCAE), version 5.0 and is described in [Appendix 4](#).

The investigator is responsible for ensuring that all adverse events observed by the investigator or reported by the subject that occur after first dose of investigational product(s)/study treatment/protocol-required therapies through the end of study are reported using the Event CRF.

9.2.3.1.1.3 Serious Adverse Events

The investigator is responsible for ensuring that all serious adverse events observed by the investigator or reported by the subject that occur after signing of the informed consent through 20 weeks after the last administration of investigational product are reported using the Event CRF.

All serious adverse events will be collected, recorded and reported to the sponsor or designee within 24 hours, as indicated in [Appendix 4](#). The investigator will submit any updated serious adverse event data to the sponsor within 24 hours of it being available.

The criteria for grade 4 in the CTCAE grading scale differs from the regulatory criteria for serious adverse events. It is left to the investigator's judgment to report these grade 4 abnormalities as serious adverse events.

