10.3.2.3 Safety Analyses

10.3.2.3.1 Adverse Events and Disease-related Events

Subject incidence of all treatment-emergent adverse events will be tabulated by system organ class and preferred term. Tables of fatal adverse events, serious adverse events, adverse events leading to withdrawal from investigational product or other protocol-required therapies, and significant treatment-emergent adverse events will also be provided. Subject incidence of disease-related events, if applicable, will be tabulated by system organ class and preferred term.

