Both Amgen and the Investigator reserve the right to terminate the Investigator's participation in the study according to the Clinical Trial Agreement. The investigator is to

notify the IRB/IEC in writing of the study's completion or early termination and send a copy of the notification to Amgen.

Subjects may be eligible for continued treatment with Amgen investigational product(s) by an extension protocol or as provided for by the local country's regulatory mechanism. However, Amgen reserves the unilateral right, at its sole discretion, to determine whether to supply Amgen investigational product(s) and by what mechanism, after termination of the study and before the product(s) is/are available commercially.

Compensation

Any arrangements for compensation to subjects for injury or illness that arises in the study are described in the Compensation for Injury section of the Informed Consent that is available as a separate document.

Appendix 4. Safety Events: Definitions and Procedures for Recording, Evaluating, Follow-up and Reporting

Definition of Disease-related Event

Disease-related Event Definition

• Disease-related events are events (serious or non-serious) anticipated to occur in the study population due to the underlying disease. See Section 9.2.3.1.1.1 for the list of disease-related events. All serious disease-related events will be recorded and reported to the sponsor or designee within 24 hours.• Disease-related events that would qualify as an adverse event or serious adverse event:
○ An event based on the underlying disease that is worse than expected as assessed by the investigator for the subject's condition or if the investigator believes there is a causal relationship between the investigational product(s)/study treatment/protocol-required therapies and disease worsening, this must be reported as an adverse event or serious adverse event.• Disease-related events that do not qualify as adverse events or serious adverse events:
○ An event which is part of the normal course of disease under study (eg, disease progression in oncology or hospitalization due to disease progression) is to be reported as a disease-related event.

Definition of Adverse Event

Adverse Event Definition

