**Part B:**

**For Part B of this study, the actual treatment will be defined as follows:**

- **If a subject receives placebo throughout the Part B of this study, the actual treatment will be defined as placebo**
- **If a subject receives at least one dose of tezepelumab in Part B of this study, the actual treatment will be defined as the highest dose of tezepelumab the subject receives**

Treatment-Emergent Adverse Events

Events categorized as Adverse Events (AEs) including events reported as **Disease Related Events** starting on or after first dose of investigational product as determined by **“Did event start before first dose of investigational product” equal to “No” or missing on the Events eCRF (including either “adverse event” or “disease related event” record on eCRF) and up to End of Study Date.**

Disease Related Events

**Disease-related events are events (serious or non-serious) anticipated to occur in the study population due to the underlying disease as recorded on the Events eCRF page. Details on disease related events can be found in protocol Appendix 4.**

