**Summary** of serious adverse events will be tabulated by system organ class, preferred term **grade and relatedness.**

**A separate disease related events listing will be provided.**

In addition, subject incidence of Events of Interest (EOI) will also be summarized. EOI will be identified using an Amgen Standardized MedDRA Query (AMQ) for the following:

**Exposure-adjusted event rate and exposure adjusted incidence rate will be reported from day 1 to week 52 only in Part A, in the final analysis.**

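### The SAP pools disease-related events into the TEAE tables and replaces their incidence table with a listing, so TEAE totals would favour the drug if atopic dermatitis events are commoner on placebo

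*SAP*

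**What the plan says.** **SAP.** The TEAE definition in section 5.1 opens with "Events categorized as Adverse Events (AEs) including events reported as" and goes on to name disease-related events. It takes in both record types on the Events eCRF, with no filter on severity or relatedness. Section 9.6.1 lists incidence tables for TEAEs, serious events, events leading to withdrawal of investigational product, and fatal events, and then says "Adverse events and disease related events will be summarized together". For disease-related events on their own it says "A separate disease related events listing will be provided".

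**Protocol.** Section 9.2.3.1.1.1 says "Disease-related events pre-defined for this study include AD". Appendix 4 draws a line within that class:

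- "An event based on the underlying disease that is worse than expected as assessed by the investigator", or one that the investigator believes is causally related to treatment, must be reported as an adverse event or serious adverse event.
- Under the label "Disease-related events that do not qualify as adverse events or serious adverse events" it places "An event which is part of the normal course of disease under study", which is reported as a disease-related event.

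Section 10.3.2.3.1 describes the TEAE, fatal, serious and withdrawal tables and then adds: "Subject incidence of disease-related events, if applicable, will be tabulated by system organ class and preferred term".

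**Recorded departures.** The visible text of SAP section 10 covers the added POEM and EQ-5D-3L objectives and a change to an event-of-interest definition. It mentions neither the pooling nor the loss of the disease-related incidence table. Part of the section is redacted.

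**The concern.** The safety endpoint is subject incidence of adverse events, compared with placebo. AD activity is what the drug is meant to reduce: the sample size section assumes EASI response of 15% on placebo and 50% on 420 mg Q2W. If that is roughly right, normal-course AD events should be recorded more often on placebo. Counting them as TEAEs puts an efficacy outcome into the safety comparison, and it works in the drug's favour.

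The rows at risk are those that add across terms: any TEAE, the skin system organ class, and the grade, seriousness and withdrawal totals. The exposure-adjusted event rates are also at risk if they use the TEAE definition, because each repeated flare adds to the count. A reader of the study report would have no by-arm incidence of disease-related events with which to undo the pooling, only a listing.

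**Working it through.** **1. Texts side by side.**

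| Question | Protocol | SAP |
|---|---|---|
| Is a normal-course AD event an adverse event? | No (Appendix 4) | Counted as a TEAE (5.1, 9.6.1) |
| Is AD that is worse than expected, or believed related, an adverse event? | Yes (Appendix 4) | Yes |
| Output for disease-related events | Incidence by system organ class and preferred term (10.3.2.3.1) | Listing only (9.6.1) |
| Is the change recorded? | n/a | Not in the visible text of section 10 |

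The conflict is confined to normal-course events. The protocol's condition that the table be applicable is met, because AD is named as a disease-related event.

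**2. Size of the shift.** The documents give no figure to reproduce, and no AD event rates or other adverse event rates by arm. All rates below are assumptions. Let *a* be the proportion with at least one other adverse event and *d* the proportion with at least one AD event recorded only as disease-related. If the two are independent within an arm, pooled incidence is 1 − (1 − *a*)(1 − *d*).

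*No true difference, a = 50% in both arms:*

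- AD 30% placebo, 15% drug: 1 − 0.50 × 0.70 = 65.0% and 1 − 0.50 × 0.85 = 57.5%, an apparent 7.5-point advantage for the drug.
- AD 40% and 10%: 1 − 0.50 × 0.60 = 70.0% and 1 − 0.50 × 0.90 = 55.0%, 15 points.
- AD equal in both arms: no shift.

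The 30%/15% case depends on overlap. If every AD event falls in a subject who also has another adverse event, both arms show 50% and there is no shift. If they fall in different subjects, the totals are 80% and 65%, 15 points.

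*True excess of 15 points on drug (a = 40% placebo, 55% drug):*

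| AD placebo / drug | Pooled placebo | Pooled drug | Difference, independent | Difference, different subjects |
|---|---|---|---|---|
| 15% / 10% | 49.0% | 59.5% | +10.5 | +10 |
| 25% / 10% | 55.0% | 59.5% | +4.5 | 0 |
| 30% / 10% | 58.0% | 59.5% | +1.5 | −5 |
| 40% / 10% | 64.0% | 59.5% | −4.5 | −15 |

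With full overlap the difference stays at +15 in every row. With *a* = 50% and 65%, the independent differences are +11.0, +6.0, +3.5 and −1.5. Under independence and 10% AD on drug, the excess vanishes when placebo AD reaches 1 − (0.45 × 0.90)/0.60 = 32.5%, or 1 − (0.35 × 0.90)/0.50 = 37% in the second case.

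**3. Skin system organ class row.** Assume AD is coded there, and other skin events are 5% on placebo and 12% on drug (+7 points). With AD at 25% and 10%, the pooled row reads 1 − 0.95 × 0.75 = 28.75% and 1 − 0.88 × 0.90 = 20.8%, or −7.95 points. With AD at 15% and 10% it reads 19.25% and 20.8%, or +1.55 points.

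**4. Rows not affected.** AD coded to its own preferred term leaves every other preferred-term row unchanged.

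**The case against.** **The protocol is not one-sided.** Its synopsis speaks of AD as a disease-related adverse event. Appendix 4 counts the exacerbation of a chronic condition as meeting the adverse event definition, allows signs and symptoms arising from lack of efficacy to be reported if they meet that definition, and excludes only day-to-day fluctuation that does not worsen. So a worsening flare can properly be an adverse event. This stands: only normal-course records are wrongly added, and their number is unknown.

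**No separate table is promised in so many words.** A reader might infer one, but 10.3.2.3.1 does not use that word, and the AD preferred-term row in the pooled table would supply much of the content. This stands in part. That row mixes normal-course AD with AD reported as an adverse event, so it does not give disease-related incidence as such.

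**The direction is assumed.** A reader might take it as fact that placebo subjects have more AD events, or that the pooling does hide a drug excess. The documents show neither. They give no AD rates by arm, and the earlier phase 2a study missed its primary endpoint.

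**Precision is low anyway.** With 60 per arm, the standard error for 55% against 40% is √[(0.55 × 0.45 + 0.40 × 0.60)/60] = 9.0 points, a 95% half-width of about 18. Even a 15-point excess would be uncertain in a clean table, and specific toxicities would be sought in the preferred-term and event-of-interest rows. This stands, but it does not justify a systematic shift in the totals.

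**Pooling has a purpose.** It keeps the TEAE count from depending on the investigator's view of what is worse than expected or related. If the drug worsened AD and this was recorded only as disease-related, tables without those records would miss it. This is a good reason to keep the pooled tables.

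**Conclusion.** The conflict between SAP and protocol is in the text, the protocol's disease-related incidence table has become a listing, and the visible text of SAP section 10 does not record the change.

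The bias is conditional. If AD events are commoner on placebo, totals that add across terms shift toward the drug; preferred-term rows do not. The illustrations run from no shift (full overlap) to 15 points where there is no true difference. A true 15-point excess appears as anything from +15 to −15. Those figures rest entirely on assumed rates and assumed overlap, so they show what is possible and do not estimate what will happen.

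Two stronger readings are not supported: that the headline comparison is shown to be biased, and that the pooled tables should be dropped or demoted in favour of tables without disease-related records. The definition is openly stated in the SAP, and pooling guards against misclassification. The change is still worth making, because it restores an analysis the protocol describes and takes an efficacy-driven component out of the adverse event comparison.

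**What to change.** Amend the SAP before database lock:

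1. Present TEAE, SAE and withdrawal incidence by arm without records reported only as disease-related events. AD that is worse than expected or judged related stays in, because Appendix 4 requires it to be reported as an adverse event or SAE.
2. Add a by-arm incidence table of disease-related events by system organ class and preferred term, as in protocol 10.3.2.3.1.
3. Keep the pooled tables alongside, labelled as including disease-related events, and state which definition the exposure-adjusted rates use.
4. Record any remaining departure from the protocol in SAP section 10.

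The Events eCRF already distinguishes the two record types, so no new data are needed. The cost is a few extra tables. The drawback is that the non-pooled totals depend on how investigators classify AD events, which is why both sets should be shown.

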**Summary** of serious adverse events will be tabulated by system organ class, preferred term **grade and relatedness.**

**A separate disease related events listing will be provided.**

In addition, subject incidence of Events of Interest (EOI) will also be summarized. EOI will be identified using an Amgen Standardized MedDRA Query (AMQ) for the following:

**Exposure-adjusted event rate and exposure adjusted incidence rate will be reported from day 1 to week 52 only in Part A, in the final analysis.**

#### **9.6.2 Laboratory Test Results**

**Absolute value and change from baseline of continuous laboratory parameters will be summarized descriptively by treatment group at each visit.**

Grade 0 through 4 toxicities, as defined by the **Common Terminology Criteria Adverse Events (CTCAE)** version 5.0 (or later) will be presented for each laboratory parameter when available. **Central laboratory normal reference ranges will be used for the identification of individual clinically important abnormalities. A shift table will be produced for toxicity grade shifts, not low, normal, high values.** Shift tables will be created for hematology, immunoglobulins and IgE.

**In addition, Creatine Kinase (CK) and liver function test (LFT) abnormalities will be assessed by the incidence overall and by visits of the following categories:**

- **CK > 5 × ULN**
- **CK > 10 × ULN**
- **ALT or AST > 3 × ULN**
- **ALT or AST > 5 × ULN**
- **INR > 3**
- **Total bilirubin > 2 × ULN**
- **(ALT or AST > 3 × ULN) and Total bilirubin > 2 × ULN and ALP < 2 × ULN**

### 9.6.3 Vital Signs

**Absolute value and change from baseline value will be summarized descriptively by treatment group at each visit.** If there is an unexpected safety finding, vital signs will be flagged and summarized descriptively as baseline disease summaries.

### 9.6.4 Physical Measurements

Height and weight will be summarized descriptively as baseline summaries.

### 9.6.5 Electrocardiogram

**The electrocardiogram (ECG) measurements from this clinical study were performed as per standard of care for routine safety monitoring, rather than for purposes of assessment of potential QT interval corrected (QTc) effect. Because these evaluations may not necessarily be performed under the rigorous conditions expected to lead to meaningful evaluation of QTc data, neither summaries nor statistical analyses will be provided, and these data would not be expected to be useful for meta-analysis with data from other trials.**

### 9.6.6 Antibody Formation

**The number and percentage of subjects with binding and neutralizing anti-tezepelumab antibodies will be summarized by treatment group, if applicable.**

### 9.6.7 Exposure to Investigational Product

Descriptive statistics will be produced to describe the exposure to **IP** by treatment group, **for Part A and B respectively.**

### 9.6.8 Exposure to Non-investigational Product

Descriptive statistics will be produced to describe the exposure to TCS by treatment group.

### 9.6.9 Exposure to Concomitant Medication

The number and proportion of subjects receiving therapies of interest (TCS and TCI) will be summarized by **preferred term or category for each treatment group as coded by the World Health Organization Drug (WHO DRUG) dictionary.**

## 9.7 Other Analyses

### 9.7.1 Analyses of Pharmacokinetic or Pharmacokinetic/Pharmacodynamic Endpoints

**All subjects randomized to tezepelumab treatment groups will have pharmacokinetic samples assessed. Descriptive statistics of tezepelumab serum concentrations by treatment group and visit will be provided. Summary of mean**

and individual serum tezepelumab concentrations by treatment group will be summarized in tables and/or figures and provided. Additional PK/PD analysis and exposure-response analysis may be performed as needed and reported separately.

#### 9.7.2 Analyses of Clinical Outcome Assessments

Analyses of COA endpoints are covered in [Section 9.5.2](#) and [Section 9.5.3](#).

#### 9.7.3 Analyses of Health Economic Endpoints

Analyses of COA endpoints are covered in [Section 9.5.2](#) and [Section 9.5.3](#)

#### 9.7.4 Analyses of Biomarker Endpoints

For skin swabs for *S. aureus* testing, the number of subjects with positive response will be summarized by treatment group and visit.

Other biomarker analysis will be conducted if interest arises.

### 10. Changes From Protocol-specified Analyses

Exploratory objectives “To explore the effect of tezepelumab on POEM” and “To explore the effect of tezepelumab on EQ-5D-3L” were not originally specified in the protocol, but are added here for completeness in analysis of patient reported outcomes.

In protocol Section 9.2.3.1.5, [REDACTED]

[REDACTED]” is removed, because study database does not provide the attribute.

Instead, a modification is made in this SAP [Section 9.6.1](#) as the following:

“EOI will be identified using events within the system organ class (SOC) of

[REDACTED]” and which meet the following criteria:

[REDACTED]

## **12. Prioritization of Analyses**

Two interim analyses will occur when approximately the 80th and 160th subjects are projected to complete week 16 assessments in Part A. The trial (both Part A and B) will be stopped for futility **based on the results of either interim analyses**.

Primary analysis will be performed when all randomized subjects complete week 16 assessments in Part A.

Exploratory analysis for Part B will occur when all randomized subjects complete week 16 assessments in Part B.

Final analysis will occur at the end of study date.

**13. Appendices**

### Appendix A. Analytical Window for Evaluation

Per protocol, visits are to be performed within 3 days of the protocol-specified study day. To allow for variations in scheduling, the following visit windows will be applied to selected efficacy and safety evaluations (ie, vital signs, laboratory evaluations) to assign a most appropriate nominal visit for analysis. If more than one assigned visit falls within the same defined window, the closest visit to the target day (ie, scheduled visit week  $\times$  7 + 1) will be considered for analysis. If two assessment dates are the same distance from the target day, then the latest visit will be considered for analysis. If more than one evaluation falls on the same date and time for laboratory results, then the value with the smallest accession number will be used.

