^m Administration of study drug is the final activity performed at a visit. Subjects randomized to Q4W dosing will receive placebo at the visits between dosing with tezepelumab. Subjects will be observed for 2 hours post-treatment at the day 1 and week 2 visits. For all other visits where investigational product is administered, subjects will be observed for a period of time at the discretion of the Investigator.

ⁿ All subjects will receive a 420 mg SC dose of either study drug or placebo as their first dose.

^o Only certain inclusion criteria specified in the protocol will be re-evaluated at the day 1 visit. These criteria will be evaluated prior to any other day 1 study activities and are required to be met for dosing with investigational product.

^p All subjects who terminate the study early will complete an early termination visit consisting of all assessments included in the EOT (week 52) visit. In addition, a safety follow-up visit will occur 18 weeks after the EOT visit.

Table 2-2. Schedule of Activities for Part A and Part B (Week 26 Through End of Study)

	Treatment Period (52 weeks) ^a														EOT ^a /ET ^l	EOS ^a		Unscheduled
	Wk 26	Wk 28	Wk 30	Wk 32	Wk 34	Wk 36	Wk 38	Wk 40	Wk 42	Wk 44	Wk 46	Wk 48	Wk 50	Wk 52	Wk 58	Wk 70		
GENERAL AND SAFETY ASSESSMENTS																		
Physical examination															X	X	X	X
12-lead ECG ^b																	X	X
Vital signs ^c	X	X	X	X	X	X	X	X	X	X	X	X	X	X	X	X	X	X
Adverse events	X	X	X	X	X	X	X	X	X	X	X	X	X	X	X	X	X	X
Serious adverse events	X	X	X	X	X	X	X	X	X	X	X	X	X	X	X	X	X	X
Disease-related events	X	X	X	X	X	X	X	X	X	X	X	X	X	X	X	X	X	X
Concomitant therapies review	X	X	X	X	X	X	X	X	X	X	X	X	X	X	X	X	X	X
LABORATORY ASSESSMENTS																		
Urine pregnancy test ^d		X		X		X		X		X		X		X		X		X
Coagulation													X	X				X
Hematology						X						X		X	X	X		X
Chemistry						X						X		X	X	X		X
Urinalysis (dipstick) ^e						X						X		X	X	X		
Anti-tezepelumab-antibody						X						X					X	X
Serum immunoglobulins ^f					X							X		X				X
PPD or Quantiferon GOLD														X				
STUDY-SPECIFIC ASSESSMENTS																		
Electronic diary ^g	Completed in the morning at home on eDiary																X	X
Assessment of EASI and IGA						X							X	X	X		X	
SCORAD						X							X	X	X			
EQ-5D-3L, POEM, DLQI, PGI-S						X							X	X	X			
Tracking of TCS use (Part B subjects only)	X	X	X	X	X	X	X	X	X	X	X	X	X	X	X	X	X	X

Footnotes defined on last page of the table

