9.1.4 End of Study

The EOS visit will occur 18 weeks after the EOT visit (20 weeks after the final dose of study drug) and is the same as the safety follow-up visit.

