### **9.5.1 Analyses of Primary Efficacy Endpoint(s)**

#### **9.5.1.1 Primary Analysis of the Primary Endpoints**

[figure not shown]
The primary analysis of the primary estimands as defined in [Section 2.1](#) will be performed using the FAS – Part A. Primary endpoints are defined in [Section 5.5](#). **Where an endpoint cannot be derived due to missing IGA or EASI assessments, a patient will be assumed not to have achieved the outcome, that is, Non-Responder Imputation (NRI).**

Treatment effect **for IGA 0/1 at week 16** will be tested using a logistic regression model with baseline IGA as covariate. **Similarly, treatment effect for EASI 75 at week 16 will**

**be tested using a logistic regression model with baseline EASI as covariate.** From **each** model, odds ratio and 95% CIs will be reported, comparing each tezepelumab dose group to placebo.

To control the family-wise type 1 error rate at 0.05 (**2-sided**) for the multiple comparisons of 420 mg vs. placebo and 280 mg vs. placebo, the hypotheses **described in Section 2.2** will be tested using a Bonferroni-based gatekeeping chain procedure (**Dmitrienko 2013**) as shown in [Figure 9-1](#). This procedure will split alpha of 0.05 equally to test in parallel tezepelumab 420 mg SC Q2W versus placebo and tezepelumab 280 mg SC Q2W versus placebo for IGA 0/1 and EASI 75 sequentially within each parallel **dose** path. If one of the parallel **dose** paths rejects **the 2** hypotheses sequentially, and the other **dose** path has at least one hypothesis not rejected, then the unspent  $\alpha$  of 0.025 from the successful path will be propagated to the **unsuccessful dose path** to retest the 2 hypotheses sequentially at a level of 0.05.

Figure 9-1. Alpha Split Between Two Doses of Interest

In addition, analysis of primary endpoints may be considered using mFAS-Part A as a supporting analysis to examine the impact of COVID-19 2020 outbreak on outcomes without multiplicity adjustment.

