**Analysis Windows for Anti-Tezepelumab Antibodies**

Visit Week	Target Day	Window Definition
Baseline	1	
Week 12	85	Study Day 2 to 126
Week 24	169	Study Day 127 to 210
Week 36	253	Study Day 211 to 294
Week 48	337	Study Day 295 to 413
Week 70	491	Study Day 414 to 494

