**Analysis Windows for Serum Immunoglobulins**

Visit Week	Target Day	Window Definition
Baseline	1	
Week 16	113	Study Day 2 to 175
Week 34	239	Study Day 176 to 287
Week 48	337	Study Day 288 to 350
Week 52	365	Study Day 351 to 368

Note: If more than one visit (including the unscheduled visits) falls within the same defined window with non-missing measurements, scheduled visit will be used regardless of the distance from the target day. Unscheduled visit will only be used when there is no measurement from scheduled visit in the defined window.

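### SAP Appendix A assigns visits by study day alone, so an early leaver's off-drug safety follow-up visit is filed under a treatment-period week instead of follow-up

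*SAP*

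**What the plan says.** The opening text of SAP Appendix A states that "visit windows will be applied to selected efficacy and safety evaluations (ie, vital signs, laboratory evaluations) to assign a most appropriate nominal visit for analysis". Each table then gives a range of study days per nominal week. The rules for competing records are few. "If more than one assigned visit falls within the same defined window, the closest visit to the target day" is the one used, with the later visit on a tie and the smallest accession number for same-time laboratory results. A note under the serum immunoglobulin table adds: "Unscheduled visit will only be used when there is no measurement from scheduled visit in the defined window". No rule refers to last dose, early termination or follow-up.

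The last row in the vitals, EASI/IGA, pregnancy-test, haematology/chemistry/urinalysis and antibody tables is week 70, target day 491. For antibodies that row is "Study Day 414 to 494". It starts at day 428 for EASI/IGA and pregnancy tests, and at day 449 for vitals and haematology/chemistry/urinalysis.

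The protocol ties the visit to when the subject leaves. Under the Schedule of Activities (Section 2.2), early terminators complete the week-52 assessments at an ET visit. "In addition, a safety follow-up visit will occur 18 weeks after the EOT visit". Section 9.1.4 identifies the EOS visit with this one and also times it as "20 weeks after the final dose of study drug) and is the same as the safety follow-up visit".

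SAP 9.6.2 and 9.6.3 summarise laboratory values and vital signs by treatment group at each visit. For the primary endpoints, where a missing IGA or EASI prevents derivation, SAP 9.5.1.1 says "a patient will be assumed not to have achieved the outcome" (non-responder imputation, NRI). SAP 8.3.2 extends NRI to the modelled secondary and exploratory IGA/EASI responder endpoints.

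**The concern.** The week-70 row fits the follow-up visit only for someone treated to the end. A subject who leaves at week 12 and returns 18 weeks later is seen at about week 30, with no drug for some 20 weeks. The rule as written files that record under a week that the protocol's schedule places in the 52-week treatment period.

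Two things are at stake. First, by-visit vitals and laboratory rows would mix washed-out values with values from subjects still on schedule, while the follow-up row would lose most early leavers who did attend. Second, in the exploratory week 24/36/52 responder analyses, a withdrawn subject would be imputed as a non-responder at most weeks but count as observed at one week, chosen only by the date of departure.

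**Working it through.** **Inputs.** Follow-up interval: 18 weeks = 126 days (Protocol 2.2, 9.1.3, 9.1.4). Windows: SAP Appendix A. Visit tolerance: ±3 days (Protocol 2.2).

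**Reproducing the plan's target day.** Week × 7 + 1 gives 70 × 7 + 1 = 491. This equals EOT day 365 + 126 = 491, and also last dose at week 50 (day 351) + 140 = 491. The week-70 target is therefore the follow-up day of a subject who completes treatment.

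**Mapping for early leavers.** Follow-up day = ET day + 126. It falls in a treatment-period row when ET day ≤ (end of last treatment-period window) − 126.

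| Evaluation | Last treatment-period window ends | ET limit | ET days sent to week 58 | Week 70 reached from ET day |
|---|---|---|---|---|
| Vitals; haematology, chemistry, urinalysis | 385 (week 52) | 385 − 126 = 259 | 260–322 | 323 |
| Antibodies | 413 (week 48) | 413 − 126 = 287 | no such row | 288 |
| EASI/IGA; pregnancy test | 427 (week 52) | 427 − 126 = 301 | no such row | 302 |

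A follow-up visit 3 days early or late moves these limits by 3 days.

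**EASI/IGA in detail.** ET days 2–14 map to week 16, 15–84 to week 24, 85–168 to week 36, 169–217 to week 48, 218–231 to week 50 and 232–301 to week 52.

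**Example.** ET at week 12 is day 85, so follow-up is day 85 + 126 = 211. EASI/IGA, laboratory and antibody records become week 36 (window 211–294). Vitals become week 30 (204–217).

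**Does another record displace it?** For ET days 2 to 364, the ET and follow-up visits never share a window in any of these tables. With no other visit in the window, the follow-up value is the one selected. The preference for scheduled visits does not help, because the follow-up is itself scheduled.

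**Share affected (assumption: ET days uniform over the 363 days from 2 to 364).** Vitals and laboratory: (259 − 1)/363 = 258/363 = 71% in treatment-period rows, 63/363 = 17% in week 58, 42/363 = 12% in week 70. Antibodies: 286/363 = 79% in treatment-period rows. EASI/IGA: 300/363 = 83%.

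**Ceiling on counts (assumptions: 10%, 20% or 30% of the 240 Part A subjects terminate early, and all attend follow-up).** 24, 48 or 72 × 258/363 = about 17, 34 or 51 subjects in treatment-period laboratory rows. With lower attendance the number falls, to zero if none return.

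**Week 16.** The EASI/IGA window is days 99–140, so ET + 126 enters it only for ET by day 140 − 126 = 14. Such a subject would normally have had only the day-1 dose. Timed at 20 weeks after that dose, the visit is on day 1 + 140 = 141, which is in the week-24 window.

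**Does another section correct it?** SAP 5.2 defines the EOS date but gives no windowing rule. SAP 5.4 to 5.6 remove values only after TCS/TCI rescue from day 29. SAP 8.3.2 acts only on missing values. The truncation in 9.5 and 9.5.3.1 covers only data after the switch to 420 mg.

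One input is inferred: the columns of Protocol Table 2-2 are shifted in the text available to me, so EASI/IGA at the EOS visit is taken from the SAP's own week-70 row for it.

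**The case against.** The strongest reply is that few subjects are exposed and that off-drug values are not foreign to this plan. Most of it stands as a limit on size.

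- Subjects who only stop drug are told to keep to the visit schedule (Protocol 7.1.5, 7.4.2.1, 8.1), so those who do are seen at week 70 as planned. A reader might infer that people stopping for adverse events vanish from the follow-up row. An adverse event is listed as a reason to stop product (8.1), not as a reason for removal from the study (8.2.2).
- Of the four reasons for removal in 8.2.2, withdrawn consent, death and loss to follow-up make a return visit unlikely or impossible. Any count is therefore a ceiling.
- A reader might infer that off-drug IGA/EASI values contradict the estimand. They do not: SAP 2.1 counts outcomes whether or not treatment is completed, and the treatment-period rows will hold other off-drug values by design. The objection here is to one displaced visit.
- An observed non-response and NRI both count as zero. A responder rate moves only if the displaced value is a response without TCS/TCI rescue. Post-switch truncation also removes some records from the Part A repeated-measures models and descriptive summaries.
- For antibodies, SAP 9.6.6 specifies no by-visit table, and Protocol 9.2.8 makes testing conditional, so that consequence is weak.
- Week 58 is also a post-treatment visit. It would be wrong to add its 17% to the 71% and call the total treatment-period mislabelling.

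None of this changes where the rule sends the vitals and laboratory records of those who do return.

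**Conclusion.** The point holds as a wrong assignment rule with a limited effect. For subjects who leave the study early and still attend the safety follow-up, Appendix A labels that visit as a treatment-period week for ET up to about day 259 (vitals, haematology, chemistry), 287 (antibodies) or 301 (EASI/IGA).

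The main effect is on descriptive by-visit vitals and laboratory tables and on the week-70 row, which keeps only subjects who completed or left late. The secondary effect is on the exploratory week 24/36/52 IGA/EASI results. Adverse event incidence does not use these windows.

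It is tempting to read this as a threat to the primary endpoint. The documents do not support more than a marginal effect there: it needs ET by about day 14 and a visit timed from ET rather than from last dose, or one to three days early. On the uniform assumption that is 13/363, or 3.6%, of early terminators.

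The day limits rest on follow-up at exactly ET + 126 days. The percentages also rest on uniform ET timing, and the number of affected subjects cannot be derived from the documents.

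**What to change.** Add to SAP Appendix A, in words such as: *Assessments at the safety follow-up (EOS) visit are assigned by CRF visit label to a Safety follow-up row, whatever the study day, and are not eligible for the treatment-period windows.* That row replaces Week 70 in every table that has one. ET visits stay windowed by study day. Apply the same rule to IGA/EASI, so that an early leaver with no other assessment in the window is missing and the existing missing-data handling applies.

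The SAP already uses a visit label where a day rule would mislead: in Section 5.3, baseline IGA and EASI must come from the Day 1 visit. The cost is one sentence and one condition in the windowing program. The downside is a few fewer observed records at some treatment-period weeks.
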